2. RATIONALE

As is common with new therapies for rare conditions, the EMA has required a post-authorisation safety study (PASS) to further evaluate the safety profile of brentuximab vedotin. Specifically, this PASS is designed as a prospective, observational cohort study including patients prescribed brentuximab vedotin as part of routine clinical care and followed for up to five years for the occurrence of selected safety outcomes. In addition to SAEs, the following both serious and non-serious adverse events of special interest (AESI) will specifically be evaluated as part of the PASS: peripheral neuropathy, neutropenia (including febrile neutropenia), infections (including opportunistic infections), hyperglycaemia and hypersensitivity reactions (including infusion-related reactions and allergic reactions). In addition to the overall patient population, to the extent possible, the safety profile of brentuximab vedotin in elderly patients and patients with longer term exposure (i.e., ≥ 16 cycles) will also be evaluated. The study is intended to provide important information regarding the safety profile of brentuximab vedotin in a real-world population.

3. OBJECTIVES

The objectives of the study are to:

- Evaluate the occurrence of serious adverse events (SAEs) and specified adverse events
 of special interest (AESI), both serious and non-serious, in patients actively treated for
 relapsed or refractory CD30+ HL or relapsed or refractory sALCL in routine practice
 with brentuximab vedotin; and
- Identify and describe potential risk factors for peripheral neuropathy in relapsed or refractory CD30+ HL or relapsed or refractory sALCL patients treated with brentuximab vedotin.

4. STUDY DESIGN

4.1 Study Description

This is a multi-center international prospective, observational cohort study of patients who have been diagnosed with relapsed or refractory CD30+ HL or relapsed or refractory sALCL and are treated with brentuximab vedotin as part of routine clinical care. The study will target the enrolment of approximately 500 patients (at least 50 of whom have a diagnosis of sALCL), who are initiating or are currently being treated with brentuximab vedotin at approximately 75-100 sites in 12-15 countries in Europe and potentially in other countries outside of Europe. Patients already being treated with brentuximab vedotin at the time of enrolment will be considered to be retrospectively enrolled for purposes of analysis and inclusion in the PASS. The sample size for this study was based on the need for more information regarding the occurrence of both serious and non-serious AESI, relative to the

Confidential. Page 15 of 44

size of the current safety database. The study will continue for five years from the date of first patient enrolled. The study will be managed by the contract research organization (CRO) Quintiles, with oversight by Millennium Pharmaceuticals, Inc. (Millennium) project team.

Sites that treat patients with relapsed or refractory CD30+ lymphomas including HL and sALCL will be invited to participate in the study. Country and site selection will depend on the timing of commercial availability of brentuximab vedotin, reimbursement status, and physician product adoption rates in the selected countries to ensure that an adequate number of patients treated with brentuximab vedotin are available for enrolment into the study. The duration of the enrolment period may be extended (or contracted) based on actual patient accrual rates.

Eligible patients will be identified from sites where patients are initiating or already receiving therapy with brentuximab vedotin. No study specific visits or procedures will be required as part of patient participation in the study. Patients will be evaluated according to the physician's standard practice and discretion.

4.2 Study Population

The study will aim to enrol eligible patients with relapsed or refractory CD30+ HL or sALCL, from approximately 75-100 centers in Europe (and possibly additional countries outside of Europe). It is estimated that approximately 500 patients (at least 50 of whom have a diagnosis of sALCL) will be eligible and agree to participate during the planned approximate 3-year enrolment period of the study. The sample size for this study was based on the need for more information regarding the occurrence of both serious and non-serious AESI, relative to the size of the current safety database (refer to Section 5.1 regarding the sample size justification). Patients already being treated with brentuximab vedotin at the time of enrolment will be considered to be retrospectively enrolled for purposes of analysis and inclusion in the PASS.

To the extent possible, enrolment of all eligible patients at each site is expected in order to ensure representativeness of the study population.

4.2.1 Inclusion Criteria

To be eligible for enrolment, patients must meet all of the following criteria:

- Age at enrolment ≥ 18 years
- Clinical diagnosis (with histologic confirmation) of relapsed or refractory CD30+ HL or relapsed or refractory sALCL
- Patient is planned to start or is already receiving single agent therapy with brentuximab vedotin as part of routine clinical care

Confidential. Page 16 of 44

• Willing and able to provide informed consent

4.2.2 Exclusion Criteria

Patients meeting ANY of the following criteria are not eligible for participation:

- Concurrent participation in an interventional clinical study
- Patients with primary cutaneous ALCL, unless the disease has transformed to systemic ALCL

4.2.3 Study Enrolment

Oncologists and haematologist-oncologists who are routinely involved in the care and treatment of patients with relapsed or refractory CD30+ HL and sALCL will be targeted for recruitment. Site selection criteria will include the projected availability of eligible patients in a 36-month enrolment period and the capacity of site staff to complete the case report forms (CRFs). Selection criteria and basic site information (e.g., practice size, investigator specialty, site type) will be collected via a site qualification survey.

Eligible patients will be invited to provide informed consent to participate in the study at the time of presentation for a routine clinic visit. No specific clinic visits are required as part of participation in this study. All assessments are intended to be based on routine patient care or by referencing the medical records.

All patients presenting during the enrolment period will be assessed for eligibility according to the defined selection criteria and all eligible patients will be invited to participate in the study. A screening log will be maintained by each site to record the disposition of patients potentially eligible for study participation, in order to better assess the representativeness of the sampled population. Minimal, non-identifiable information will be recorded for all patients who are screened for study enrolment, but no patient-identifiable information should be recorded. To formally address the concern of selection bias for the retrospective patients, the reasons will be collected, if possible, for each patient who received brentuximab vedotin and was not enrolled.

4.2.4 Patient Withdrawal and Treatment Discontinuation

Patients may withdraw consent and discontinue participation in the study at any time, with no effect on their medical care or access to treatment. If a patient is withdrawn prior to completing the study follow-up period, any known reason for withdrawal should be documented in the database. All information already collected as part of the study will be retained for analysis; however, no further efforts will be made to obtain or record additional information regarding the patient. If the last assessment was more than three months prior to withdrawal from study and patient status has not been documented, if possible a final

Confidential. Page 17 of 44

assessment of treatment status and any SAEs and both serious and non-serious AESI (per Section 7.2 Procedures for Recording and Reporting SAEs and AESI) should be recorded at the time of withdrawal from study.

All patients who permanently discontinue brentuximab vedotin should continue to be followed according to the protocol's recommended recording of essential data.

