4.5 Data Collection

4.5.1 Schedule of Recommended Recording of Essential Data

Essential data for the study are presented in the Schedule of Recommended Recording Essential Data provided in Table 1. For eligible patients who provide informed consent, data elements will be abstracted from information routinely recorded in the medical record. Follow-up data will be collected in conjunction with all routine care visits, typically occurring at approximately every three months. No study visits or examinations, laboratory tests or procedures are mandated as part of this study.

Confidential. Page 19 of 44

Table 1 Schedule of Recommended Recording of Essential Data

	Enrolmenta	On-Treatment Follow- up ^b	Post-Treatment Follow-up ^c (or study discontinuation)
Informed consent	X		
Demography	X		
Patient height & weight	X	X (weight only)	
ECOG Performance Status	X	X	
Relevant medical history & co-morbidities	X	X	
Laboratory test results (if performed as part of routine care)	X	X	
Relapsed or refractory CD30+ HL or sALCL disease and treatment history	X	X	
Brentuximab vedotin treatment details	X	X	
Concomitant medications	X	X	
Changes in treatment, including dose modifications		X	
Survival status			X
SAE and AESI recording in eCRF (Refer to section 7.2) ^d	X	X	
Both SAEs and AESI considered related to brentuximab vedotin - recording in eCRF (Refer to Section 7.2) ^d			X
Date and reason for discontinuation (if applicable)		X ^e	X ^e

^a Exposure to brentuximab vedotin may have started prior to enrolment. All brentuximab vedotin treatment and concomitant medication exposures, SAEs/AESI and relevant medical history since starting the current brentuximab vedotin regimen should be recorded at the time of enrolment.

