4.5.5 Study Discontinuation

The following data will be recorded, where available, for all enrolled patients at the time of discontinuing the study:

- Date of discontinuation
- Reason for discontinuation
- Updated assessments as outlined in Table 1, which depend on whether the patient is in the On-Treatment Follow-up or Post-Treatment Follow-up period
- Survival status

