5.2.2 Planned analyses

5.2.2.1 Primary analyses

Serious Adverse Events (SAEs) and Adverse Events of Special Interest (AESI)

SAEs and AESI (including both serious and non-serious AESI) will be summarized by MedDRA system organ class (SOC) and preferred term (PT). Frequency and incidence proportion for all SAEs and AESI (as defined in Section 4.4.1) will be reported for patients who received at least one dose of brentuximab vedotin while on study.

The incidence rate and the associated 95% CI will be reported for SAEs and AESI.

Time at risk of SAEs and AESI will correspond to current/recent treatment with brentuximab vedotin. Current/recent treatment will be defined as time between the dates of first and last dose plus 30 days. All other follow-up time accrued for the patient will be considered occurring during past treatment with brentuximab vedotin; events reported during the past treatment period will be presented separately.

In addition, select events will be displayed by timing in relation to treatment start (e.g., by number of completed cycles) or time-to-event analysis may be carried out using Kaplan-Meier plots for the occurrence of the first reported occurrence of the adverse event, as appropriate for the event.

Identification and Description of Risk Factors for Peripheral Neuropathy

In addition, multivariable adjusted analysis will be performed to identify and describe risk factors for peripheral neuropathy (e.g., BMI, previous history of neuropathy, known toxic exposures) in the cohort. Risk factors for the first occurrence of new onset or worsening of peripheral neuropathy will be explored using a multivariable adjusted Cox regression model. Model assumptions concerning proportionality will be evaluated graphically in the usual manner. The inclusion of specific risk factors will be described in the SAP. A preliminary univariate analysis of the association of variables of interest with the outcome measure will be

Confidential. Page 24 of 44

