7.2.1 Events to be recorded in the eCRF

All SAEs and both serious and non-serious AESI will be recorded in the eCRF, from the patient's first dose of brentuximab vedotin through 30 days after the patient's last dose of brentuximab vedotin. For retrospectively enrolled patients, this includes any SAEs or both serious and non-serious AESI identified in the medical record which occurred prior to study enrolment but after initiating the current regimen of brentuximab vedotin. From 31 days after the patient's last dose of brentuximab vedotin, only SAEs and both serious and non-serious AESI considered related to brentuximab vedotin will be recorded in the eCRF (see Table 3).

Documentation regarding an SAE or both serious and non-serious AESI, observed by the investigator or reported by the patient upon indirect questioning, should be made as to the

Confidential. Page 31 of 44

nature, date of onset, end date, severity, relationship to brentuximab vedotin, action(s) taken, and outcome.

If any of the same SAE or both serious and non-serious AESI, occur on several occasions in the same patient, then the event in question must be documented and assessed each time.

7.2.2 Events to be reported to Millennium Pharmacovigilance & Risk Management (PV&RM) or designee (in addition to being recorded in the eCRF)

All SAEs (regardless of relationship to brentuximab vedotin) and both serious and non-serious AESI considered related to brentuximab vedotin, occurring from the patient's first dose of brentuximab vedotin in the current regimen through 30 days after the patient's last dose of brentuximab vedotin, must also be reported to Millennium PV&RM or designee by faxing a completed SAE Form within one business day after becoming aware of the event (see Table 3). For retrospectively enrolled patients, this includes any SAEs (regardless of relationship to brentuximab vedotin) or AESI, both serious and non-serious, considered related to brentuximab vedotin identified in the medical record which occurred prior to study enrolment but after initiating the current regimen of brentuximab vedotin.

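### Sections 4.2.4 and 4.5.5 give conflicting rules for recording SAEs and AESI at study withdrawal, and the 4.2.4 exception would seldom apply between on-schedule visits

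*Protocol*

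**What the plan says.** **Section 4.2.4 (withdrawal).** Data already collected are kept, but "no further efforts will be made to obtain or record additional information regarding the patient". The exception follows: "If the last assessment was more than three months prior to withdrawal from study and patient status has not been documented, if possible a final" "assessment of treatment status and any SAEs and both serious and non-serious AESI" should be recorded. Two conditions must hold together (a gap of more than three months, and status undocumented), and even then the request is qualified.

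**Section 4.5.5 (study discontinuation).** "The following data will be recorded, where available, for all enrolled patients at the time of discontinuing the study". The list includes "Updated assessments as outlined in Table 1, which depend on whether the patient is in the On-Treatment Follow-up or Post-Treatment Follow-up period". There is no condition on the time since the last assessment.

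**Section 7.2.1 (event recording).** "All SAEs and both serious and non-serious AESI will be recorded in the eCRF, from the patient's first dose of brentuximab vedotin" until 30 days after the last dose; after that, only related events. A recent assessment creates no exception.

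**Section 4.5.1 (timing).** "Follow-up data will be collected in conjunction with all routine care visits, typically occurring at approximately every three months".

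**Table 1, footnote e.** For the data due at study discontinuation it sends the reader to Section 4.5.4. That section covers post-treatment follow-up and lists only related SAEs and AESI. The discontinuation list is in 4.5.5.

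**The concern.** A site handling a withdrawal finds two instructions. The section named for withdrawal tells it to collect nothing more unless the gap is long and status is unknown; the section on discontinuation tells it to update the assessments for everyone. The cross-reference that should settle the matter points to the wrong section.

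The three-month threshold also equals the typical collection interval. A patient who leaves between two on-schedule visits is within three months of the last one, so the 4.2.4 exception does not operate in the ordinary case.

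At stake is the completeness of SAE and AESI recording, which is the study's first objective. The new-onset or worsening neuropathy used in the Cox model could also be affected. Completeness would depend on which section a site happened to follow.

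**Working it through.** The protocol states no figure on this point, so there is none to reproduce.

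**Step 1: the rules side by side.** Take a patient on treatment who withdraws six weeks after the last data collection, with status not documented since.

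| Section | What it asks for in those six weeks |
|---|---|
| 4.2.4 | Nothing: six weeks is less than three months |
| 4.5.5 | Updated on-treatment assessments, where available, including SAEs and AESI |
| 7.2.1 | All SAEs and AESI to last dose plus 30 days |

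The instructions differ for the same patient.

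**Step 2: how often the 4.2.4 trigger is met.** Let X be the interval between assessments in months, and let withdrawal fall at a random time between visits. Then

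- share of withdrawals more than three months after the last assessment = E[(X − 3)+] / E[X];
- mean time since the last assessment, over all withdrawals = E[X²] / (2E[X]), which is (9 + SD²)/6 when the mean interval is 3.

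The mean of 3 months is from Section 4.5.1. The spread is assumed (gamma-distributed intervals unless stated), because the protocol gives none.

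| Intervals, mean 3 months | Share past three months | Mean time since last assessment |
|---|---|---|
| Fixed | 0% | 9/6 = 1.5 months |
| SD 0.25 | 3% | 9.0625/6 = 1.51 |
| SD 0.5 | 7% | 9.25/6 = 1.54 |
| SD 1 | 13% | 10/6 = 1.67 |
| SD 1.5 | 20% | 11.25/6 = 1.88 |
| Exponential (SD 3) | e⁻¹ = 37% | 18/6 = 3.0 |

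If the true interval is fixed but longer, the share is (m − 3)/m: 0.5/3.5 = 14%, 1/4 = 25%, 2/5 = 40%, 3/6 = 50%. If visits are one or two months apart, the share is 0% and the mean gap is 0.5 or 1 month. These shares are upper limits for the trigger, because the undocumented-status condition must hold as well.

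**Step 3: which events could be missed.** Section 7.2.2 requires all SAEs, and all related AESI whether serious or not, from first dose to last dose plus 30 days, to go to the sponsor within one business day of the site learning of them, in addition to the eCRF entry. Later, the same applies to related events. So, if 4.2.4 is followed:

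| Event since the last assessment | Already due under 7.2.2? |
|---|---|
| SAE known to the site, on treatment | Yes |
| Related AESI known to the site | Yes |
| Non-serious AESI judged unrelated, on treatment | No |
| Any event in the record not yet noticed | Not until noticed |

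**Step 4: effect on the estimates.** An incidence proportion loses any event that is missed. For the incidence rate, Section 5.2.2.1 states: "Current/recent treatment will be defined as time between the dates of first and last dose plus 30 days". The treatment-status update is part of the same final assessment. If it is skipped, doses since the last assessment generally go unrecorded too, and person-time and events are cut together, apart from a tail of up to 30 days after the last recorded dose.

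**The case against.** **The sections can be read together.** One may say that 4.2.4 is the specific rule for withdrawn consent and 4.5.5 the general one, limited to available data. But 4.2.4 itself allows a look-back when the gap is long, so the line it draws is elapsed time, not consent. Section 7.2.1 contains no such carve-out, and footnote e does not lead to the right list. The conflict stands.

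**A severe reaction or worsening neuropathy before withdrawal would be left blank.** A reader might infer this, but if the event was serious, or was an AESI judged related, and the site knew of it, Section 7.2.2 already required a report. The objection succeeds here: the gap is narrower, as Step 3 shows.

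**The loss is concentrated in patients leaving because of toxicity.** A reader might infer this too, but it confuses stopping the drug with leaving the study. Section 4.2.4 keeps patients who stop brentuximab vedotin in follow-up, and the study mandates no visits or tests that a toxicity would give reason to refuse. Outcome-related withdrawal is possible but not shown.

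**Person-time runs on without events, so rates are clearly biased downward.** Step 4 limits this to a short tail in most cases. Missed events can still lower the proportions.

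**The interval may be shorter in practice.** Data are collected at all routine visits, and three months is only typical. If infusion attendances count as routine visits, the gap is shorter. Median exposure in the phase 2 studies was about 27 and 20 weeks (Section 1), against follow-up of up to five years, so much follow-up is post-treatment, where only related events are recorded. Both points reduce the size; neither removes the conflict.

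**Conclusion.** The protocol contradicts itself on what to record at withdrawal, and this is plain from the text without any assumption. That the 4.2.4 trigger would seldom be met between on-schedule visits follows from the threshold matching the collection interval. The figures of 0% to 20%, or 37% in the extreme case, rest on a three-month mean interval, assumed spreads and withdrawal at a random time. A patient who withdraws at a visit loses nothing.

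The consequence is a probably small under-ascertainment that depends on the section a site follows. It falls mainly on non-serious AESI judged unrelated and on events not yet noticed. A reader might be tempted to size it from an assumed withdrawal rate, but the protocol states none, so no count of patients or person-years can be supported. This is an inexpensive correction worth making, not a threat to the study's main estimates.

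**What to change.** Reconcile Sections 4.2.4, 4.5.5 and 7.2.1, and the Table 1 footnote, in one amendment:

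- In 4.2.4, remove the three-month and undocumented-status conditions. State that, for every withdrawing patient, treatment status (with the date of last dose) and SAEs and AESI from the last assessment to the withdrawal date are recorded from the existing medical record, under the period rules of Section 7.2, where available and as far as consent allows. Nothing is collected for the time after that date.
- Correct Table 1 footnote e to point to Section 4.5.5 instead of 4.5.4.

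The cost is a short change of wording and one chart look-up per withdrawal. Section 4.5.5 already implies that look-up, and 4.2.4 already allows it after longer gaps. No visit or test is added.

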4.3 Exposure Definition and Measures

This is an observational study of real-world treatment practices in this patient population. This protocol does not recommend the use of any specific treatments. No study medication is provided as part of participation.

Patients will be enrolled after the patient agrees to participate and signs the informed consent form. All exposure to brentuximab vedotin (including any exposure prior to enrolment) will be collected.

As an observational study to understand safety in patients treated in the post-marketing setting, no restrictions on concomitant treatments are associated with the study. All concomitant treatments (and subsequent treatments for lymphoma during follow-up) will be carefully recorded in order to evaluate their potential influence on the outcomes of interest.

